## 9.3.2. Regulatory Reporting for Studies Conducted Under DMID-Sponsored IND

Following notification from the investigator, DMID, the IND sponsor, will report any suspected adverse reaction that is both serious and unexpected. DMID will report an AE as a suspected adverse reaction only if there is evidence to suggest a causal relationship between the drug and the AE. DMID will notify FDA and all participating investigators (i.e., all investigators to whom the sponsor is providing drug under its INDs or under any investigator's IND) in an IND safety report of potential serious risks from clinical trials or any other source, as soon as possible, but in no case later than 15 calendar days after the sponsor determines that the information qualifies for reporting as specified in 21 CFR Part 312.32. DMID will also notify FDA of any unexpected fatal or life-threatening suspected adverse reaction as soon as possible but in no case later than 7 calendar days after the sponsor's initial receipt of the information. Relevant follow-up information to an IND safety report will be submitted as soon as the information is available. Upon request from FDA, DMID will submit to FDA any additional data or information that the agency deems necessary, as soon as possible, but in no case later than 15 calendar days after receiving the request.

All serious events designated as "not related" to study product(s), will be reported to the FDA at least annually in a summary format.

#### 9.3.3. Reporting of Pregnancy

Pregnancies occurring in study subjects will be reported in IDES. No further treatment will be administered to pregnant subjects, but all study-mandated blood samples will be obtained and the subject will continue in follow-up for safety events (see Section 7.6). In addition, pregnant subjects will no longer undergo pelvic exams or swabs collection. Pregnancies will be followed to pregnancy outcome pending the subject's permission.

# 9.4. Type and Duration of Follow-up of Subjects after Adverse Events

AEs will be followed until resolved or subject is considered stable.

# 9.5. Halting Rules

Study enrollment and dosing will be halted and an ad hoc DSMB review will be performed if any of the following occur at any time during the study:

#### **Study Halting Events:**

1. One or more subject experiences a treatment-related SAE.

- 2. One or more subject experiences vulvar and/or vaginal ulceration, abscess, or necrosis associated with study product administration.
- 3. Two or more subjects experience a treatment-related severe (Grade 3) unsolicited adverse event.
- 4. Three or more subjects who received at least one treatment dose experience the same severe (Grade 3) solicited AE as evaluated by a licensed clinician.
- 5. Three or more subjects who received at least one treatment dose experience a severe (Grade 3) study related laboratory abnormality in the same laboratory parameter.
- 6. An overall pattern of symptomatic, clinical, or laboratory events that the DMID, Medical Monitor, or DSMB consider associated with study product and that may collectively represent a serious potential concern for safety.

# 9.6. Safety Oversight (ISM plus DSMB)

## 9.6.1. Data and Safety Monitoring Board

Because this is a large Phase II Randomized Clinical Trial, a DSMB will be created to review this study. The DSMB will be composed of three to four members and may include at least one physician involved in research, one biostatistician and potentially an expert in the field of microbiology. This committee will be charged with reviewing the protocols with respect to ethical and safety standards and making recommendations if necessary. During the studies, the Committee will meet (either in person, via teleconference or web-based meetings) at least annually to review safety issues and to monitor center performance in execution of the protocol.

Prior to each meeting, a formal, detailed report will be generated with emphasis placed on safety issues.

A formal DSMB review will occur after 30 subjects have received at least one dose of study drug and have completed Visit 2. The DSMB will either recommend continued enrollment of the remaining subjects or discontinuation of enrollment. Though the timing of the DSMB review will be expedited, enrollment may continue while awaiting the DSMB review. In addition, a computerized system will be used to acquire any data regarding halting criteria throughout the study.

Additionally, a single fully blinded interim analysis is planned to reassess the adequacy of the sample size based on subjects meeting eligibility for the Modified Intent-to-Treat (mITT) cohort (see also Section 11). After eighty subjects have been enrolled and have available test results for Nugent score, HIV, chlamydia and gonorrhea, the fraction of subjects who are enrolled to date who are eligible for the mITT cohort will be estimated. Based on this calculation, the enrollment target may be increased from 120 subjects to a maximum of 150 as required to achieve the target of 90 subjects eligible for the mITT cohort. The study sponsor and investigators will have access to the data shared in fully blinded reports issued to the DSMB.

If any of the halting rules are met, the study will not proceed with the remaining enrollment without a review by and recommendation from the DSMB to proceed. Upon completion of this review and receipt of the advice of the DSMB, DMID will determine if study entry or study dosing should be interrupted or if study entry and study dosing may continue according to the protocol.

The study is masked. The DSMB has the option to request unmasking to make determinations regarding study outcome.

# 9.6.2. Independent Safety Monitor (ISM)

Safety oversight for this study will include an ISM in close proximity to each of the clinical research sites. The ISM will receive and evaluate SAEs blinded and provide an independent written summary to the DMID Clinical Project Manager and DMID Medical Monitor. The ISM may be asked by the DMID Medical Monitor to review additional safety events (i.e. significantly increased frequency of non-serious adverse events).

## 10. CLINICAL MONITORING

# 10.1. Site Monitoring Plan

Site monitoring will be conducted to ensure that human subject protection, study procedures, laboratory procedures, study intervention administration, and data collection processes are of high quality and meet sponsor, International Conference on Harmonisation (ICH)/Good Clinical Practice (GCP) guidelines and applicable regulatory requirements, and that the study is conducted in accordance with the protocol and sponsor's standard operating procedures. The DMID or its designee will conduct site-monitoring visits as specified in the monitoring plan.

Monitoring visits will include, but are not limited to, review of regulatory files, accountability records, CRFs, informed consent forms (ICFs), medical and laboratory reports, and protocol compliance. Study monitors will meet with investigators to discuss any problems and actions to be taken and document visit findings and discussions.

## 11. STATISTICAL CONSIDERATIONS

#### 11.1. Introduction

This is a Phase 2, double-blind, randomized, placebo-controlled, multi-center trial comparing 5% Monolaurin Vaginal Gel to Vehicle Placebo Gel as outpatient therapy. A total of 120 eligible subjects with BV will be enrolled. Treatment assignments will be randomly allocated in a 2:1 ratio of test article to placebo, with the randomization stratified by clinical site. Each subject will receive intravaginal gel twice daily for three successive days for a total of 6 doses. There will be 3 clinic visits over 31 days.

## 11.2. Data Analysis Populations

The Per-Protocol (PP) efficacy analysis population includes all randomized subjects who met all inclusion/exclusion criteria, did not have any significant protocol deviations, complied with the assigned study treatment, returned to the study site for the Test of Cure visit within the specified window (Visit 2 Study Day 8 relative to the first day of treatment [Window: Days 8-15]), or discontinued study product early due to lack of treatment effect or received vaginosis or systemic antimicrobial therapy other than study drug during the study. Subjects with Visit 1 test results including a grade 3 laboratory abnormality, a positive Visit 1 HIV, *Chlamydia*, or *Neisseria gonorrhoeae* test, a PAP result consistent with HSIL, AGUS, or CIN2 or greater, or a Visit 1 Nugent score < 4 will excluded from the PP population.

A subject is compliant with study treatment if she uses at least 5 of 6 doses of study product, as assessed by the study coordinator's count of used / unused applicators in each returned subject kit. If a kit is not returned, compliance will be assessed by the subject's self-report on the memory aid. Significant protocol deviations include sexual intercourse including receptive oral sex or insertion of substances or objects intravaginally between Visit 1 and Visit 2.

The Modified Intent-to-Treat (mITT) efficacy analysis population includes all randomized subjects who met all inclusion/exclusion criteria excluding those who have a Nugent score <4 at Visit 1 or are positive for other concomitant vulvovaginal infections at baseline which may interfere with the efficacy assessment. The mITT population will be used as the primary analysis population for the test of 5% Monolaurin Vaginal Gel to Vehicle Placebo Gel.

The Evaluable efficacy analysis population includes all subjects in the mITT population who received study treatment and returned for at least one post-baseline visit.

The Intent-to-Treat (ITT) efficacy analysis population includes all randomized subjects.

The safety population includes all randomized subjects who received at least one dose of study product.

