# 11.3. Study Objectives and Endpoints

The primary study objectives are to compare 5% Monolaurin Vaginal Gel with vehicle placebogel (excipients only) with respect to 1) safety and tolerability, and 2) efficacy by clinical cure at Visit 2. The primary safety outcome measures are the number of subjects reporting solicited urogenital AEs following the first dose of the study product through Visit 2 (Days 8-15) and the number of

Failure

Not Evaluable

subjects reporting SAEs considered product related following the first dose of study product through Visit 3 (Day 22-31). The primary efficacy outcome measure is the proportion of subjects with clinical cure in each study arm at Visit 2 (Days 8-15).

A clinical cure is defined by normal Amsel criteria. Normal Amsel criteria are defined as: normal physiological vaginal discharge, whiff test negative for any amine "fishy" odor, saline wet mount less than 20% for clue cells, and vaginal pH is <=4.5.

A clinical failure is defined by a) one or more abnormal Amsel criteria, b) early discontinuation of study therapy due to lack of treatment effect, c) use of any vaginosis therapy other than study product during the study, or d) in the investigators opinion, requires additional treatment for vaginosis.

Subjects who do not meet the criteria for either the clinical cure or clinical failure definitions are not evaluable for clinical cure.

A secondary efficacy outcome measure is the proportion of subjects with therapeutic cure in each study arm at Visit 2 (Day 8-15) and at Visit 3 (Day 22-31). Therapeutic cure is defined as both a clinical cure AND a bacteriological cure (Nugent score 0-3). Subjects who were clinical failures, or have a Nugent score >3 are therapeutic failures. Subjects who are not evaluable for clinical cure, or do not have a Nugent score result are not evaluable for therapeutic cure.

If the clinical cure outcome is	and the Nugent (bacteriological) score result is	then the overall therapeutic cure outcome is
Cure	0-3	Cure
Cure	>3	Failure
Cure	Not Evaluable	Not Evaluable
Failure	0-3	Failure
Failure	>3	Failure
Failure	Not Evaluable	Failure
Not Evaluable	0-3	Not Evaluable

 Table 3:
 Bacterial Vaginosis: Determination of Therapeutic Cure

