6.3.5. Per Protocol Population

The Per Protocol (PP) population for all endpoints measured at Visit 2 includes all randomized subjects who met all inclusion/exclusion criteria, did not have sexual intercourse including receptive oral sex or insertion of substances or objects intravaginally between Visit 1 and Visit 2, complied with the assigned study treatment, returned to the study site for the Test of Cure visit within the specified window (Visit 2 Study Day 8 relative to the first day of treatment [Window: Days 8-15]), or discontinued study product early due to lack of treatment effect or received vaginosis or systemic antimicrobial therapy other than study drug before Visit 2. Subjects with

Visit 1 test results including a grade 3 laboratory abnormality, a positive Visit 1 HIV, Chlamydia, or *Neisseria gonorrhoeae* test, are found to have a PAP result consistent with HSIL, AGUS, or CIN2 or greater, or a Visit 1 Nugent score < 4 will be excluded from the PP population. A review of medical history and concomitant medications will be performed to identify any other infections that may interfere with the efficacy assessment. Subjects with these identified infections will be excluded from the PP population.

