4. If answer to 'Inserted any intravaginal substances or objects other than the study treatment? ' is 'Yes', then concatenate answer to the substances that were inserted : Tampons, Spermicide, Douche, Diaphragm, Feminine deodorant product, Other: Other, specify. For example, if a subject marked Yes to Tampons, Douche and Other, where other specify is metronidazole gel, this column would be: Yes [Substances: Tampons, Douche, Other: metronidazole gel]. If answer is 'No' or 'Unknown', there will be no answer to substances.

				Subject Report		Clinic Assessment of Product Accountability		
Subject ID	Randomized Treatment Group	Actual Treatment Group	Number of Doses Taken as Scheduled	Number of Doses Taken Out of Window	Number of Doses Not Taken	Returned Used Applicators	Returned Unused Applicators	
XXXXXX	5% Monolaurin Vaginal Gel/Placebo Gel	5% Monolaurin Vaginal Gel/Placebo Gel	x	x	x	x	x	
xxxxxx	5% Monolaurin Vaginal Gel/Placebo Gel	5% Monolaurin Vaginal Gel/Placebo Gel	x	X	X	x	x	
XXXXXX	5% Monolaurin Vaginal Gel/Placebo Gel	5% Monolaurin Vaginal Gel/Placebo Gel	x	x	x	x	x	

Listing 9: 16.2.5 Compliance Data - Safety Population

1. Sort order is Subject ID.

2. Total number of doses is 6. Number of doses not taken will be calculated as 6 - Number of doses taken as scheduled - Number of doses taken out of window.

3. A dose will be considered 'Taken as Scheduled' on a given day if there are 2 doses taken on the same day at least 8 hours a part. The doses should be taken within 72 hours from first dose at least 8 hours apart and not more than 2 doses in a 24 hour period to be counted as all 6 being 'Taken as Scheduled''. If only one dose is taken on a day, then the first dose will be considered 'Taken as Scheduled'. If the first dose is taken after 3 pm, then only 1 dose will be taken on Day 1 and 1 dose on Day 4. Otherwise, a subject should have 2 doses taken on Day 1, 2 doses taken on Day 2 and 2 doses taken on Day 3. Any doses taken outside these time limits will be considered to be 'Taken Out of Window'.

4. If a subject does not have a record for 'Returned Used Applicators' or 'Returned Unused Applicators', then an 'Unknown' will be placed in those columns.

Subject ID	Randomized Treatment Group	Actual Treatment Group	Analysis Population	Visit Number	Study Day	Clinical Cure	Bacteriologic Cure	Therapeutic Cure
xxxxxxx	5% Monolaurin Vaginal Gel/Placebo Gel	5% Monolaurin Vaginal Gel/Placebo Gel	ITT, mITT, Evaluable, PP	xx	XX	Y/N	Y/N	Y/N

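### The per-protocol definition contradicts itself: an unbracketed 'or' seems meant to keep early failures, but the dose, insertion and window rules and the SAP Table 4 shell would exclude many of them

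*Protocol*

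**What the plan says.** Protocol 11.2 builds the PP population from four conditions: all entry criteria met, no significant deviation, compliance with treatment, and return for the test of cure in window. The sentence then runs on: "or discontinued study product early due to lack of treatment effect or received vaginosis or systemic antimicrobial therapy other than study drug during the study".

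The same section fixes two of those conditions:
- Dosing: "A subject is compliant with study treatment if she uses at least 5 of 6 doses of study product".
- Deviations: "Significant protocol deviations include sexual intercourse including receptive oral sex or insertion of substances or objects intravaginally between Visit 1 and Visit 2".

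A separate sentence removes women with certain Visit 1 results (grade 3 laboratory value, positive HIV, chlamydia or gonorrhea test, abnormal PAP). It ends "or a Visit 1 Nugent score < 4 will excluded from the PP population".

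Protocol 11.3 makes most of the women named in the clause clinical failures. Its definition includes "early discontinuation of study therapy due to lack of treatment effect, c) use of any vaginosis therapy other than study product during the study". SAP 3.3.3 (c) widens this to systemic antimicrobial therapy.

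SAP 6.3.5 keeps the construction for the Visit 2 set, ending "or discontinued study product early due to lack of treatment effect or received vaginosis or systemic antimicrobial therapy other than study drug before Visit 2", and for the Visit 3 set with the period running between Visits 1 and 3. SAP 3.3.9 adds timing limits to the dose rule. SAP 3.3.8 excludes from PP anyone who returns outside Days 8-15.

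**The concern.** The women in the clause are treatment failures whose outcome is known, and the clause reads as an attempt to keep them in the PP denominator. No bracket shows what the *or* replaces, and none of the dose, insertion or window rules exempts them. The SAP Table 4 shell goes further and lists early stopping for lack of effect, and systemic antimicrobial therapy, as reasons for exclusion from PP. A programmer working from SAP 6.3.5 and one working from Table 4 could build different PP sets.

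PP is one of the populations in which the primary endpoint is re-tested with its own Fisher p-value (Protocol 11.4; SAP 8.1, Table 29). It is also used for the secondary and exploratory outcomes and for the recumbent-position analysis (SAP 8.2, 8.3, 10). If membership is settled only after unblinding, the choice can depend on the data.

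**Working it through.** **Step 1. The clause against the other rules.**

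| Rule | Effect on women the clause names | Exemption stated? |
|---|---|---|
| At least 5 of 6 doses (Protocol 11.2; SAP 3.3.9) | A woman who stops early has used fewer than six doses, so she qualifies only with exactly five | No |
| No insertion between Visits 1 and 2 (Protocol 11.2; SAP 6.3.5) | Removes those who used an intravaginal vaginosis therapy before Visit 2 | No |
| Return within Days 8-15 (SAP 3.3.8) | Removes those who return outside the window | No |
| SAP Table 4 shell | Lists early stop for lack of effect, systemic antimicrobial therapy and fewer than five doses as exclusion reasons | Opposite of SAP 6.3.5 for the first two |

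Two of the three first-line regimens in Protocol 2.1 are intravaginal. In SAP Appendix III, the worked example for Listing 8 records an inserted substance "where other specify is metronidazole gel". The rule in Protocol 11.3 that drops non-evaluable women does not explain the removals, because a clinical failure is evaluable.

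**Step 2. The two readings.**
- *Narrow:* criteria AND no deviation AND compliant AND (in-window return OR early stop OR other therapy). Early failures with fewer than five doses, or with intravaginal therapy before Visit 2, drop out. Those with five or more doses and oral therapy can stay. Arm cure rates rise.
- *Wide:* (all four conditions) OR early stop OR other therapy. Women enter without meeting the eligibility, deviation, dosing or window conditions. The separate Visit 1 exclusions, and the SAP's other-infection exclusion, still apply. Under SAP 3.3.3 all who enter this way are failures, so cure rates fall.

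**Step 3. Size.** The plan gives no figure for this point: no expected number of early failures and no expected PP size. As a setting I take the planned mITT arms of 60 and 30 and the two-sided 5% Fisher test (Protocol 11.4 and 11.5). Full enumeration of that test gives power .783 for cure rates of .50 versus .20, against .78 in Protocol Table 4, so the test is implemented as planned.

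With x cures among n women, dropping d failures gives x/(n - d) and adding d failures gives x/(n + d). Cure counts and d are assumed.

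| Base | Change (active, placebo) | Active | Placebo | Difference | p |
|---|---|---|---|---|---|
| 30/60 v 6/30 | none | .500 | .200 | .300 | .007 |
| | drop 6, 3 | 30/54 = .556 | 6/27 = .222 | .333 | .005 |
| | drop 6, 0 | 30/54 = .556 | 6/30 = .200 | .356 | .0025 |
| | drop 1, 6 | 30/59 = .508 | 6/24 = .250 | .258 | .0496 |
| | add 6, 0 | 30/66 = .455 | 6/30 = .200 | .255 | .023 |
| 18/60 v 3/30 | none | .300 | .100 | .200 | .038 |
| | drop 1, 1 | 18/59 = .305 | 3/29 = .103 | .202 | .061 |
| 24/60 v 12/30 | none | .400 | .400 | 0 | 1.00 |
| | drop 6, 3 | 24/54 = .444 | 12/27 = .444 | 0 | 1.00 |

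Dropping failures always raises an arm's rate and adding them always lowers it. The difference can rise, fall or stay put. In the 18/60 example the difference hardly moves. The p-value crosses .05 because the exact test is discrete at these counts.

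**The case against.** The best defense is that this is loose drafting in a secondary population and touches few women. Treatment is six doses over three days, with the first observed in clinic (Protocol 7.1). To fail the dose rule, a woman must stop for lack of effect before dose five. Other vaginosis therapy is reserved for clinical failures (Protocol 6.6), and the planned referral point is Visit 2 itself (Protocol 7.2), so intravaginal therapy before Visit 2 should be uncommon. A clause that specifically admits women given vaginosis therapy may also be read as overriding the general insertion rule, and the Listing 8 example is a formatting note, not a population rule.

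Much of this stands. The numbers may be small, and the insertion conflict is the weaker part of the case. It does not answer the dose rule, the window rule or the Table 4 shell, which are stated rules that point the other way.

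Several stronger conclusions are tempting, and the documents do not support them:
- *PP cure rates are biased.* This needs at least one such woman, and the direction depends on the reading and on the split between arms.
- *Women enter PP regardless of eligibility.* The Visit 1 exclusions stand in their own sentence and hold on any reading.
- *All early failures drop out.* On the narrow reading only some do.
- *Everyone admitted by the wide reading is a failure.* That follows from SAP 3.3.3 (c). Under Protocol 11.3 (c) only vaginosis therapy counts, so a woman given a systemic antimicrobial for another reason could be a cure.
- *The trial's main result is in doubt.* The primary test is in mITT. PP is one of three secondary repeats, with Evaluable and ITT.

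**Conclusion.** The PP definition is internally inconsistent in both documents, and the SAP's own table shell contradicts the SAP text. The defect lies between stated rules, so it does not depend on any assumed count. Its numerical effect does. At 30/60 versus 6/30, moving up to six failures in an arm shifted the difference from .300 to between .255 and .356 in the cases shown. With proportional dropping and no treatment effect it stayed at zero. The true number of such women is not in the documents and may be very small. The primary mITT analysis and the power table are untouched. This should be corrected before unblinding, but it does not threaten the primary conclusion.

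**What to change.** Clarify in the SAP, before unblinding. PP for Visit 2 endpoints requires all of the following:
1. all inclusion and exclusion criteria met;
2. none of the listed Visit 1 exclusions and no other interfering infection;
3. no intercourse or insertion between Visits 1 and 2, other than study product or the vaginosis therapy that itself defines the failure;
4. either (a) compliant AND an evaluable test of cure within Days 8-15, OR (b) clinical failure under SAP 3.3.3 (b) or (c) before Visit 2, including systemic antimicrobial therapy, whatever the dose count or visit timing.

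Condition 3 applies to both branches, so women with unrelated deviations do not enter merely because they failed. Use the same structure for the Visit 3 set, with failures counted up to Visit 3.

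Three alignments go with it. Give SAP 3.3.8 an exception for branch (b). Rewrite the Table 4 exclusion reasons to match the text. Reconcile Protocol 11.3 (c) with SAP 3.3.3 (c) on systemic antimicrobials. SAP Section 12 does not list that difference now, and it is the natural place to record these clarifications.

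The cost is a small SAP edit and a change to the population program. Applicator counts, insertions and other BV treatment are already collected (Protocol 6.5 and 7.2).
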